6.2. Secondary Endpoint(s)

6.2.1. Proportion of participants achieving centrally adjudicated resolution of NASH without worsening of fibrosis, at Week 48

6.2.1.1. Main Analysis

- Estimand strategy: Composite (Section 2.1.2).
- Analysis set: Evaluable (Section 4). All randomized participants who take at least 1 dose
 of investigational product who have provided evaluable baseline data for the endpoint
 (i.e. baseline biopsy data).
- Analysis methodology: For assessing dose response, the proportion of responders at Week 48 will be analyzed using a Bayesian Emax dose-response model. For assessing pairwise comparisons, the proportion of responders at Week 48 will be analyzed an using logistic regression models with treatment and baseline fibrosis stage (F2/F3) as factors (Section 5.2.1).
- Intercurrent events and missing data: If a participant discontinues treatment or from the study due to lack of efficacy or toleration prior to Week 48 or if they do not have evaluable Week 48 Biopsy data, they will be considered to be a non-responder. If they withdraw from treatment for other reasons (not related to lack of efficacy or toleration) and have evaluable biopsy data at withdrawal or Week 48, these data will be utilized to determine whether they are a responder or not.
- The number and proportion of responders for this secondary endpoint at Week 48 will be presented for each treatment arm.
- The model-estimated proportion of responders (and 90% credible interval) for each treatment arm, and the placebo-adjusted proportion of responders for BID each dose (and 90% credible interval), and odds ratio and risk difference (and corresponding 90% confidence interval) for other treatment comparisons will be presented at Week 48. For

comparisons of DGAT2i+ACCi BID doses vs corresponding DGAT2i BID monotherapy doses corresponding 50% confidence interval will also be provided.

6.2.1.2. Sensitivity/Supplementary Analysis

Sensitivity Analyses

In order to assess the sensitivity of the dose Bayesian Emax dose-response model to the location and informativeness of the prior distributions, sensitivity analyses may be performed that will utilize alternative prior distributions.

6.2.2. Proportion of participants achieving centrally adjudicated improvement in fibrosis by ≥1 stage without worsening of NASH, at Week 48

6.2.2.1. Main Analysis

- Estimand strategy: Composite (Section 2.1.2).
- Analysis set: Evaluable (Section 4). All randomized participants who take at least 1 dose
 of investigational product who have provided evaluable baseline data for the endpoint
 (i.e. baseline biopsy data).
- Analysis methodology: For assessing dose response, the proportion of responders at Week 48 will be analyzed using a Bayesian Emax dose-response model. For assessing pairwise comparisons, the proportion of responders at Week 48 will be analyzed an using logistic regression models with treatment and baseline fibrosis stage (F2/F3) as factors (Section 5.2.1).
- Intercurrent events and missing data: If a participant discontinues treatment or from the study due to lack of efficacy or toleration prior to Week 48 or if they do not have evaluable Week 48 Biopsy data, they will be considered to be a non-responder. If they withdraw from treatment for other reasons (not related to lack of efficacy or toleration) and have evaluable biopsy data at withdrawal or Week 48, these data will be utilized to determine whether they are a responder or not.
- The number and proportion of responders for this secondary endpoint at Week 48 will be presented for each treatment arm.
- The model-estimated proportion of responders (and 90% credible interval) for each treatment arm, and the placebo-adjusted proportion of responders for BID each dose (and 90% credible interval), and odds ratio and risk difference (and corresponding 90% confidence interval) for other treatment comparisons will be presented at Week 48. For comparisons of DGAT2i+ACCi BID doses vs corresponding DGAT2i BID monotherapy doses corresponding 50% confidence interval will also be provided.

6.2.2.2. Sensitivity/Supplementary Analysis

Sensitivity Analyses

In order to assess the sensitivity of the dose Bayesian Emax dose-response model to the location and informativeness of the prior distributions, sensitivity analyses may be performed that will utilize alternative prior distributions.

6.2.3. Proportion of participants achieving centrally adjudicated improvement in fibrosis by \geq 2 stages without worsening of NASH, at Week 48

6.2.3.1. Main Analysis

- Estimand strategy: Composite (Section 2.1.2).
- Analysis set: Evaluable (Section 4). All randomized participants who take at least 1 dose
 of investigational product who have provided evaluable baseline data for the endpoint
 (i.e. baseline biopsy data).
- Analysis methodology: For assessing dose response, the proportion of responders at Week 48 will be analyzed using a Bayesian Emax dose-response model. For assessing pairwise comparisons, the proportion of responders at Week 48 will be analyzed an using logistic regression models with treatment and baseline fibrosis stage (F2/F3) as factors (Section 5.2.1).
- Intercurrent events and missing data: If a participant discontinues treatment or from the study due to lack of efficacy or toleration prior to Week 48 or if they do not have evaluable Week 48 Biopsy data, they will be considered to be a non-responder. If they withdraw from treatment for other reasons (not related to lack of efficacy or toleration) and have evaluable biopsy data at withdrawal or Week 48, these data will be utilized to determine whether they are a responder or not.
- The number and proportion of responders for this secondary endpoint at Week 48 will be presented for each treatment arm.
- The model-estimated proportion of responders (and 90% credible interval) for each treatment arm, and the placebo-adjusted proportion of responders for BID each dose (and 90% credible interval), and odds ratio and risk difference (and corresponding 90% confidence interval) for other treatment comparisons will be presented at Week 48. For comparisons of DGAT2i+ACCi BID doses vs corresponding DGAT2i BID monotherapy doses corresponding 50% confidence interval will also be provided.

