2.2. Study Design

The detailed set-up of the study is summarized below -

Figure 1. Study Design

This is a multicenter, multinational, randomized, double-blind, double-dummy, placebo-controlled, parallel-group, evaluation of DGAT2i alone, and DGAT2i+ACCi. Approximately 350 participants (50 per arm) with biopsy confirmed NASH with F2-F3 fibrosis, as assessed by sponsor-identified central pathologist(s), will be randomly assigned to the study intervention to ensure approximately 280 evaluable participants (40 per arm) offer evaluable data for the primary objective.

Participants will be randomized in a balanced ratio, using a computer-generated randomization code, to receive either double-blind, double-dummy placebo, 1 of 4 doses/dosing regimens of DGAT2i alone, or 1 of 2 dose-levels of DGAT2i+ACCi for a treatment duration of up to 48-weeks.

For participants randomized before Protocol Amendment 1 is enacted, those randomized to either of the 2 QD (DGAT2i 150 mg QD and DGAT2i 300 mg QD) dosing regimens of DGAT2i alone will remain in the study but will be switched to the corresponding BID dosing regimen of DGAT2i alone, maintaining the assigned total daily dose and the double-blind, double-dummy design. New randomization to the QD treatment arms will cease, after Health Authority (where applicable) and IRB/EC approvals of Protocol Amendment 1. Therefore, following Protocol Amendment 1, participants will be randomized to one of the following treatment arms:

Placebo

DGAT2i (Ervogastat) BID dose arms (for characterization of dose-response):

- DGAT2i 25 mg BID, total daily dose of 50 mg
- DGAT2i 75 mg BID, total daily dose of 150 mg
- DGAT2i 150 mg BID, total daily dose of 300 mg
- DGAT2i 300 mg BID, total daily dose of 600 mg

DGAT2i (Ervogastat) + ACCi (Clesacostat) coadministration dose arms:

- DGAT2i 150 mg BID + ACCi 5 mg BID
- DGAT2i 300 mg BID + ACCi 10 mg BID

The treatment group labels in programmed outputs will be as follows:

Placebo	PF-5571	PF-5571	PF-5571	PF-5571	PF-5571	PF-5571	Tota1
	25 mg	75 mg	150 mg	150 mg	300 mg	300 mg	
	BID	BID	BID	BID+	BID	BID+	
				PF1304 5		PF1304 10	
				mg BID		mg BID	

Following footnote to be included on all tables: PF5571 = Ervogastat and PF1304 = Clesacostat Note: A 'Total' column is required when summarizing baseline of population randomized

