3.2. Secondary Endpoint(s)

Secondary Endpoints are:

- Proportion of participants achieving improvement in different responder definitions based on assessment by sponsor-identified central pathologist(s) at Week 48 compared to baseline (each defined as above for the primary endpoint):
 - Resolution of NASH, without worsening of fibrosis
 - Improvement in fibrosis by ≥1 stage, without worsening of NASH
 - Improvement in fibrosis by ≥2 stages (defined as a decrease of at least 2 stages in the Brunt-Kleiner scale compared to baseline), without worsening of NASH
 - Improvement of ≥2 points in Total NAS (defined as a decrease of at least 2 points in Total NAS compared to baseline), without progression of fibrosis
 - Total NAS can range from 0 to 8 and is calculated as the sum of scores of steatosis (0 to 3), lobular inflammation (0 to 3) and ballooning (0 to 2). If any of the sub-scale scores are non-evaluable/missing, then the total score should be derived as missing.
- Percent change in liver fat (assessed via MRI-PDFF in substudy population), at Week 48
- Assessment of Treatment Emergent Adverse Events (TEAEs), safety-related clinical laboratory tests, vital signs, and 12-lead Electrocardiograms (ECGs), over time up to Week 48

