The DGAT2i ED₅₀ for the histological-based primary endpoint has been assumed to be slightly higher than the projected EC₅₀ for reduction in liver fat which was estimated from a preliminary population pharmacokinetic model based on previous clinical studies with DGAT2i. Therefore, the DGAT2i ED₅₀ was estimated to be approximately 30 mg BID (TDD = 60 mg). The substantial uncertainty in ED₅₀ values was assessed in the meta-analyses of clinical dose response studies (Thomas, 2014). Therefore, based on the meta-analyses, a scaled t-distribution (with 5 degrees of freedom) is planned to be used that is focused on the initial projected ED₅₀=30 mg BID, with a scale parameter of 0.6. A normal prior distribution for the logit of the placebo response centered at logit(0.16) with a prior standard deviation of 2.0 (logistic scale) is planned to be used, which yields a weak diffuse prior distribution for the placebo response. A normal prior distribution for the Emax parameter will also be used, centred on the anticipated Emax (0.6) on the logistic scale. This prior distribution will also be diffuse on the logistic scale with a prior standard deviation of 2.0.

The proportion of primary endpoint responders in each treatment group will be analyzed by fitting a Bayesian Emax model to the data to characterize the dose response across all treatment groups and to estimate the proportion of responders (and 90% credible interval) for each dose studied, and to estimate the placebo-adjusted proportion of responders for each dose (and 90% credible interval). If an Emax model cannot be fitted to the data, then other models that allow dose response to be estimated will be fitted, i.e. linear, log-linear or exponential.

Note that a similar methodology will be used for the exploratory 'worsening from baseline' liver biopsy endpoints, but for this Estimand 3.1 will be utilized.

Pairwise Treatment Comparisons

The comparison of the proportion of responders for binary responder endpoints for DGAT2i BID doses vs placebo, and DGAT2i+ACCi BID doses vs placebo and corresponding DGAT2i BID monotherapy doses will be analyzed using logistic regression models, including baseline (SCR2 Eligibility) fibrosis stage (F2/F3) as a factor, to estimate the

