proportion of responders in each treatment group and odds ratio and risk difference (and corresponding 90% CIs) for each treatment comparison. Risk difference and 2-sided 90% confidence interval for risk difference will be calculated by using the observed placebo rate and estimated odds ratio from the logistic regression model. For comparisons of DGAT2i+ACCi BID doses vs corresponding DGAT2i BID monotherapy doses corresponding 50% CI will also be provided. No adjustment for multiple comparisons will be made.

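### The SAP has no rule for zero-event arms in the pairwise logistic regressions of two potentially sparse endpoints: fibrosis improvement by at least 2 stages (6.2.3) and dual response (6.3.2)

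*SAP*

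**What the plan says.** The 2-stage endpoint is defined in SAP 3.2 as a fibrosis improvement "defined as a decrease of at least 2 stages in the Brunt-Kleiner scale compared to baseline), without worsening of NASH". Section 6.2.3.1 compares arms by "logistic regression models with treatment and baseline fibrosis stage (F2/F3) as factors". Section 6.3.2.1 uses the same model for dual response, meaning NASH resolution together with fibrosis improvement by at least 1 stage. For both, a participant without an evaluable Week 48 biopsy is a non-responder.

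Section 5.2.1 sets the general method: "DGAT2i+ACCi BID doses vs placebo and corresponding DGAT2i BID monotherapy doses will be analyzed using logistic regression models". The risk difference and its 90% interval "will be calculated by using the observed placebo rate and estimated odds ratio from the logistic regression model". No penalised, exact or Bayesian form of the logistic model is named, so ordinary maximum likelihood is the natural reading.

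Other models do have fallbacks. If the Emax model cannot be fitted, section 5.2.1 moves to linear, log-linear or exponential curves. If the MMRM does not converge, section 5.2.2 considers compound symmetry. Section 6.6.1 uses an unconditional exact test for Tier-1 adverse events. The logistic model has no equivalent, and Appendix 4, on statistical methodology details, is marked not applicable.

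On size, SAP 2.2 plans "Approximately 350 participants (50 per arm) with biopsy confirmed NASH with F2-F3 fibrosis" so that "approximately 280 evaluable participants (40 per arm) offer evaluable data for the primary objective".

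**The concern.** Both endpoints could be sparse. To improve by 2 stages, a participant at F2 must reach F0 and one at F3 must reach F1 or F0, within 48 weeks and with no NAS component worse. Missing biopsies add failures. Under SAP 3.1, participants whose baseline biopsy is re-read as F1 stay in the analysis but cannot improve by 2 stages.

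If an arm has no events, maximum likelihood separates: the coefficient runs to plus or minus infinity and the Wald interval carries no information. The risk-difference rule then inherits the problem, most seriously when placebo is the empty arm, because the conversion multiplies an infinite odds ratio by a zero rate. Software may return a number rather than an error, so a wrong result could go into a table unnoticed. Otherwise a replacement method would be chosen after the zero cells had been seen. No hypothesis tests are planned, so these estimates and intervals are themselves the result.

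**Working it through.** **Inputs from the documents.** Seven arms, 50 randomised and 40 evaluable per arm, balanced allocation (SAP 2.2). These agree: 7 × 50 = 350, 7 × 40 = 280, and 280 / (1 − 0.20) = 350. The protocol's 89% probability concerns the primary endpoint and does not enter here.

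**Assumed input.** The event rate p. The only related figure is the 16% placebo rate for the primary composite (protocol 9.2). Both endpoints are subsets of that composite, so 16% is a ceiling for the placebo rate, not an estimate of it.

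**Chance of an empty arm.** One given arm: (1 − p)^n. At least one of seven at a common rate: 1 − [1 − (1 − p)^n]^7. For example, at 3% with n = 50, 0.97^50 = 0.218 and 1 − (1 − 0.218)^7 = 0.82.

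| Common rate | Placebo empty, n = 50 | Any of 7, n = 50 | Placebo empty, n = 40 | Any of 7, n = 40 |
|---|---|---|---|---|
| 2% | 36.4% | 95.8% | 44.6% | 98.4% |
| 3% | 21.8% | 82.1% | 29.6% | 91.4% |
| 5% | 7.7% | 42.9% | 12.9% | 61.8% |
| 8% | 1.6% | 10.3% | 3.6% | 22.4% |
| 10% | 0.5% | 3.6% | 1.5% | 9.9% |
| 16% (placebo ceiling) | 0.02% | 0.1% | 0.1% | 0.7% |

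The n = 40 columns apply if the rate refers only to those with a biopsy. An empty arm somewhere is more likely than not only below 4.6% (n = 50) or 5.7% (n = 40). For placebo itself the rate must be below 1.4% or 1.7%.

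**Unequal rates, n = 50.** The chance of any empty arm is 1 − (1 − q0)(1 − q1)^6, where q0 and q1 are the chances that placebo and one active arm are empty. Placebo 2% and active 6%: 1 − (1 − 0.364)(1 − 0.0453)^6 = 52%. Placebo 3% and active 10%: 24%.

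**Arms in the combination comparisons.** Five arms enter: placebo, 150 mg, 300 mg and both combinations. With exponent 5 and n = 50, at least one is empty with probability 90%, 71%, 33%, 7.5% and 2.6% at 2%, 3%, 5%, 8% and 10%.

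**What the model returns.** A binomial GLM was fitted to seven arms of 50 (25 F2, 25 F3), with 90% intervals. The SAP gives no conversion formula; the natural reading, with observed placebo rate p0, is RD = OR·p0 / (1 − p0 + OR·p0) − p0.

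- Placebo empty: log OR 21.8, standard error about 18,000, interval 0 to infinity. With p0 = 0 and OR infinite, the conversion is infinity times zero. Software printed 0.000 with no valid upper limit.
- One active arm empty, placebo 3/50: OR about 0, interval 0 to infinity. The conversion gives 0 − 0.06 = −6.0 points, but the upper limit fails. The other active arm checked was unaffected (OR 1, interval 0.25 to 4.02).

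**What the remedy returns.** For placebo 0/50 against active 3/50, adjusted for F2/F3, Firth regression gives OR 7.36 (90% Wald interval 0.67 to 80.5). Feeding 7.36 into the conversion still gives 7.36 × 0 / (1 + 0) − 0 = 0, so Firth alone does not repair the risk difference. The direct difference is 3/50 − 0/50 = 6.0 points, with an unadjusted Newcombe 90% interval of −0.3 to 14.1.

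**The case against.** The strongest reply is that the problem may never arise. No rate is given for either endpoint. At 8% an empty arm somewhere has probability 10%, and at 10% only 4%. A common rate also means no drug effect; if active arms respond more, the chance falls. The 75 mg and 150 mg BID groups absorb former once-daily participants, so they may exceed 50. This stands. A reader might infer that an empty arm is likely, but the documents support that only at rates that must be assumed.

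A reader might also infer that all pairwise results for the endpoint would be lost. Table 9 makes Bayesian Emax the primary method for all four monotherapy-versus-placebo comparisons, and with its priors that model stays finite when an arm is empty. Counts and proportions per arm are reported as well. An empty active arm spoils only its own contrasts. This limits the damage mainly to the combination arms. For their comparison with monotherapy, Table 9 mentions linear dose-response modelling if required, but gives no trigger or specification, so it does not close the gap.

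Nor does the point extend to the rest of section 6.3. In the three worsening endpoints (6.3.3 to 6.3.5), missing biopsies count as events. With about 10 of 50 missing, an empty arm has probability 0.8^50, about 0.00001. Endpoint 6.3.1, 1-stage improvement regardless of NAS, is broad.

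**Conclusion.** The gap is real but conditional. The SAP does not say what happens when an arm has no events in the logistic comparisons of the 2-stage and dual-response endpoints. Its risk-difference rule gives an undefined or falsely zero result if placebo is the empty arm. It would be too strong to say that the risk difference is undefined whenever any arm is empty: with an empty active arm the point estimate survives and only the interval fails.

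The size depends on an event rate absent from both documents. Over assumed common rates of 2% to 10% with 50 per arm, the chance of an empty placebo arm runs from 36% to 0.5%, and of any empty arm from 96% to 4%. These figures assume independent binomial counts; they rise if only 40 per arm can respond and fall if active arms respond more. The primary endpoint is not in question.

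**What to change.** In SAP 6.2.3.1 and 6.3.2.1, with a cross-reference from 5.2.1, specify for these two endpoints:

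- **Odds ratio:** Firth penalised logistic regression with treatment and SCR2-eligibility fibrosis stage (F2/F3) as factors, and profile-likelihood intervals at the planned 90% and, for combination versus monotherapy, 50% levels.
- **Risk difference:** a direct estimate stratified by F2/F3 with a Miettinen-Nurminen interval, replacing the conversion from the odds ratio. Both changes are needed, because a finite odds ratio applied to a zero placebo rate still returns zero.

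Apply both whatever counts are observed. Naming the endpoints avoids a sparsity threshold that someone would have to judge after unblinding. The Bayesian Emax analysis stays as it is.

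The cost is a few lines of SAP text and standard software options. Odds ratios shrink slightly. Intervals will remain wide, as the 0/50 against 3/50 example shows: the change makes the results defined and prespecified, but adds no information about a rare outcome.

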6.2.3.2. Sensitivity/Supplementary Analysis

Sensitivity Analyses

In order to assess the sensitivity of the dose Bayesian Emax dose-response model to the location and informativeness of the prior distributions, sensitivity analyses may be performed that will utilize alternative prior distributions.

6.2.4. Proportion of participants achieving centrally adjudicated improvement of ≥2 points in Total NAFLD Activity Score (NAS) without worsening of fibrosis, at Week 48

6.2.4.1. Main Analysis

- Estimand strategy: Composite (Section 2.1.2).
- Analysis set: Evaluable (Section 4). All randomized participants who take at least 1 dose
 of investigational product who have provided evaluable baseline data for the endpoint
 (i.e. baseline biopsy data).
- Analysis methodology: For assessing dose response, the proportion of responders at Week 48 will be analyzed using a Bayesian Emax dose-response model. For assessing pairwise comparisons, the proportion of responders at Week 48 will be analyzed an using logistic regression models with treatment and baseline fibrosis stage (F2/F3) as factors (Section 5.2.1).
- Intercurrent events and missing data: If a participant discontinues treatment or from the study due to lack of efficacy or toleration prior to Week 48 or if they do not have evaluable Week 48 Biopsy data, they will be considered to be a non-responder. If they withdraw from treatment for other reasons (not related to lack of efficacy or toleration) and have evaluable biopsy data at withdrawal or Week 48, these data will be utilized to determine whether they are a responder or not.
- The number and proportion of responders for this secondary endpoint at Week 48 will be presented for each treatment arm.
- The model-estimated proportion of responders (and 90% credible interval) for each treatment arm, and the placebo-adjusted proportion of responders for BID each dose (and 90% credible interval), and odds ratio and risk difference (and corresponding 90% confidence interval) for other treatment comparisons will be presented at Week 48. For comparisons of DGAT2i+ACCi BID doses vs corresponding DGAT2i BID monotherapy doses corresponding 50% confidence interval will also be provided.

6.2.4.2. Sensitivity/Supplementary Analysis

Sensitivity Analyses

In order to assess the sensitivity of the dose Bayesian Emax dose-response model to the location and informativeness of the prior distributions, sensitivity analyses may be performed that will utilize alternative prior distributions.

6.2.5. Percentage change from baseline in liver fat (assessed via MRI-PDFF) at Week 48 6.2.5.1. Main Analysis

Estimand strategy: Hypothetical (Section 2.1.2).

- Analysis set: Evaluable (Section 4). All randomized participants in the imaging substudy, who take at least 1 dose of investigational product who have provided evaluable baseline data for the endpoint, i.e. baseline MRI-PDFF data.
- Analysis methodology: For assessing dose response, the percentage change from baseline in liver fat at Week 48 will be analyzed using a Bayesian Emax dose-response model, fitted to LS means obtained from the MMRM model. For assessing pairwise comparisons, the percentage change from baseline in liver fat at Week 48 will be analyzed using an ANCOVA performed on log-transformed relative change from baseline in liver fat with treatment and baseline fibrosis stage (F2/F3) as factors, and log-transformed baseline liver fat as a covariate. All treatment effect contrasts will be obtained through fitting the Bayesian dose-response and/or exposure-response models, or an ANCOVA model (Section 5.2.2).
- Intercurrent events and missing data: Any available MRI data for all participants
 collected before or at the time of treatment withdrawal will be included in the analysis,
 but endpoint data collected after treatment withdrawal will be censored. Missing data due
 to lack of efficacy or toleration prior to Week 48 or due to other reasons (not related to
 lack of efficacy or toleration), will be assumed to be missing at random and will not be
 imputed. Instead, MMRM will be used to obtain LS mean estimate at Week 48 for each
 dose, which will then be used in fitting the Bayesian Emax model.
- The sample size, mean, standard deviation, median, minimum, and maximum at the
 baseline and postbaseline visits for observed liver fat and relative and absolute change
 from baseline will be presented for each treatment arm.
- The model-estimated mean relative changes for each treatment comparison and the
 corresponding 90% credible interval will be obtained from the model. The mean relative
 changes (RC) and their CIs will be exponentiated and percent change will then be
 determined as follows: Percent change = 100* (RC 1). For comparisons of DGAT2i +
 ACCi BID doses vs corresponding DGAT2i BID monotherapy doses corresponding 50%
 confidence intervals will also be provided.

